#### 7.5 Pharmacokinetics

Venous blood samples (4mL each) will be collected for analysis of M4112 in plasma by a validated LC-MS/MS assay. Full details of the bioanalytical method used will be described in a separate bioanalytical report.

The schedules for PK blood sampling are shown for M4112 administered as single agent (Table 4), CCI

PK parameters for M4112 will be calculated predose and over 8 h postdosing on Day 1 and Day 15, with a predose sample collected on Day 8 and predose and 2 h postdosing samples collected on Day 1 of Cycle 2.

Following analysis of M4112 concentrations, remaining plasma may be used for evaluation of potential metabolites.

CCI

The exact date/time of sample collection will be recorded in the eCRF. Although every effort should be made to collect PK blood samples according to the schedule, blood samples collected outside of the planned window are not to be considered protocol deviations as long as the actual collection time is recorded, with the exception of the predose samples, which will be considered a deviation if not collected predose.

The PK sample should be collected after ECG and vital signs are collected when scheduled at the same time.

Details of blood sample labeling, processing, storage, and shipment requirements will be described in a separate laboratory manual.

For each subject participating in the M4112 single agent dose escalation phase, a total of approximately 76 mL of blood (4 mL/sample; 19 samples over Cycle 1 and Cycle 2, Day 1) will be collected for determination of the M4112 plasma concentration.

CCI

CCI

### 7.5.1            Body Fluid(s)

Further details will be summarized in the Laboratory Manual.

### 7.5.2            Pharmacokinetic Calculations

The software to be used and PK calculations and parameters will be specified in the integrated analysis plan (iAP).

For M4112, PK calculations using standard noncompartmental analysis methods will be performed, if appropriate, using commercial software such as Phoenix® WinNonlin® (Version 6.3 or higher) at **PPD** by standard methods. Actual dates and times as recorded on the eCRF will be utilized for final analyses, however, nominal times may be used for PK determinations in support of the SMC review (See Section 8.6).

All other data handling procedures will be detailed in the iAP.

Pharmacokinetic parameters to be calculated for M4112 are specified in Table 11.

**Table 11** Pharmacokinetic Parameters for M4112

AUC 0-8	Area under the plasma concentration-time curve from time zero to 8 h postdose
C max	Maximum plasma concentration observed postdose
t max	Time to reach maximum plasma concentration
C min	Minimum observed postdose (trough) plasma concentration
AUC 0-8/dose	Area under the plasma concentration-time curve from time zero to 8 h postdose/dose
C max/dose	Maximum observed plasma concentration/dose
C min/dose	Minimum observed postdose (trough) plasma concentration/dose
R acc (AUC 0-8 )	Accumulation of the M4112 AUC 0-8 (Day 15/Day 1)
R acc (C max )	Accumulation of the M4112 C max (Day 15/Day 1)

Final PK parameters reported will be detailed in the iAP.

A population pharmacokinetic (PopPK) model will be constructed to allow for calculation of PopPK parameters for M4112 and the analysis of selected covariates. PopPK analyses will be detailed in a separate analysis plan.

Serum concentrations for **CCI** will be summarized and may be included in population PK analyses models constructed for each analyte, respectively.

**CCI**

**CCI**

**CCI**

CCI

[figure not shown]
CCI

## 7.7 Other Assessments

### 7.7.1 Anti-Drug Antibody

CCI

## 8 Statistics

### 8.1 Sample Size

A Bayesian model is applied to assist the SMC in dosing recommendations. Bayesian models will be set up for IDO monotherapy and CCI [REDACTED] separately.

For this sample size assessment, it is assumed that it is not necessary to enroll additional subjects at RP2D or MTD and no additional levels are tested (see Section 5.1).

It is anticipated that 24 to 30 evaluable subjects (6 projected dose levels with 3 to 12 subjects each) may be needed in order to test the planned dose range of IDO monotherapy. As it is not anticipated that MTD occurs in the planned dose range, DLTs are not expected to occur frequently. Therefore, the following scenario could be anticipated, assuming 2 DLTs:

- For single agent escalation: 4 dose levels with 3 subjects each and 2 dose levels with 6 subjects each.

As inherent in dose escalation studies, the sample size cannot be prespecified. The SMC will recommend doses. Dose regimens are not prespecified as it is dependent on DLTs, PK, and PD observed.

### 8.2 Randomization

Not applicable

### 8.3 Endpoints

#### 8.3.1 Primary Endpoints

##### Part IA (Dose Escalation – M4112 as Single Agent)

- DLTs in subjects receiving M4112 as single agent during the first 4 weeks (Day 1 to Day 28 of Cycle 1) of treatment
- TEAEs and TRAEs according to NCI-CTCAE 4.03 (including deaths) in subjects receiving M4112 as single agent from start of treatment up to the last Safety Follow-up Visit
- Treatment-emergent changes from baseline in clinical laboratory measures, vital signs, ECOG PS, and physical examination findings in subjects receiving M4112 as single agent up to the last Safety Follow-up Visit.

CCI

### 8.3.2 Secondary Endpoints

#### Part IA (Dose Escalation – M4112 as Single Agent)

- Plasma PK parameters for M4112:  $AUC_{0-8}$ ,  $C_{max}$ ,  $t_{max}$ ,  $AUC_{0-8}/dose$ ,  $C_{max}/dose$ , (Days 1 and 15),  $R_{acc}(AUC_{0-8})$  and  $R_{acc}(C_{max})$  (Day 15),  $C_{min}$ , and  $C_{min}/dose$  (Days 8 and 15 of Cycle 1 and Day 1 of Cycle 2)
- Slope of concentration-QTc (cQTc) regression based on time-matched ECG readings (3 or more replicates) and PK samples during Cycle 1 at Day 1 and Day 15, central tendency and outlier analyses for absolute QTcF, and delta QTc
- BOR, DOR, DCR, time to tumor response, and PFS using RECIST 1.1, up to confirmed tumor progression.

CCI

8.3.3      Other Endpoints

CCI

## 8.4 Analysis Sets

For purposes of analysis, the following populations are defined in Table 13. CCI

Table 13 Analysis Sets

Population	Description
Screening	All participants who sign informed consent.
Dose Escalation	All subjects treated in dose escalation cohorts who do not miss > 5 planned total daily doses of M4112 CCI in the first cycle (first 28 days) of the dose escalation part for other than DLT. The CCI
Safety	The Safety Analysis Set will include all subjects who receive at least 1 dose of study treatment. CCI
Concentration-QTc Analysis Set	The cQTc Analysis Set will include all subjects with at least baseline and one on treatment measurement of time-matched ECG and M4112 plasma concentration collected during the dose-escalation phase. The cQTc analysis set will be used for slope analysis of exposure response in QTc analysis.
M4112 Pharmacokinetic	All subjects from the Safety Analysis Set without major protocol deviations/violations or events that would affect PK. Subjects in the PK Analysis Set must have received at least 1 dose of M4112 and must have sufficient M4112 plasma concentration data to enable the calculation of at least 1 PK parameter. Sufficient concentration data is defined as at least 3 valid, postdose concentration points in the PK profile to obtain any PK parameter.
Pharmacodynamics	All subjects who received at least 1 dose of M4112 and provide the predose and at least 1 postdose sample for PD assessment.

ADA = anti-drug antibody; cQTc = concentration-corrected QT interval (QTc); DLT = dose-limiting toxicities; ECG = electrocardiogram; PD = pharmacodynamics; PK = pharmacokinetic.

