**CCI**

**CCI**

If the SMC decides to change the dosing regimen, a separate model will be set up or the model extended to a partial order Continual Reassessment Method.

All subjects treated in dose escalation cohorts who miss  $> 5$  planned total daily doses of M4112 **CCI** in the first cycle (first 28 days) of the dose escalation part for other than safety reasons are not eligible for DLT assessment, will not be considered in the Bayesian model and will not formally be replaced. The SMC can still be adjourned and the Bayesian model will be updated with the data from the evaluable subjects.

The target probability for the MTD suggested by the model will be 30%. If the DLT probability of a potential MTD reaches sufficient precision, the SMC will be informed.

The 2-parameter logistic regression model will be set up as follows:

The relationship between dose and toxicity rate is defined by:

$$P(DLT|d_j, \alpha, \beta) = \frac{\exp\left(\alpha + \exp(\beta) * \log\left(\frac{d_j}{d_{ref}}\right)\right)}{1 + \exp\left(\alpha + \exp(\beta) * \log\left(\frac{d_j}{d_{ref}}\right)\right)}$$

Where  $d_j \in \{100 \text{ mg}, 200 \text{ mg}, 400 \text{ mg}, 600 \text{ mg}, 800 \text{ mg}, 900 \text{ mg}\}$  (BID dosing) and  $(\alpha, \beta)$  are bivariate normally distributed and the reference dose ( $d_{ref}$ ) is 900 mg.

The following parametrization is chosen for the monotherapy prior:

$$E(\alpha) = -0.8001$$

$$E(\beta) = 0.4647$$

$$\text{Var}(\alpha) = 1.5^2, \text{Var}(\beta) = 1.5^2, \text{Cov}(\alpha, \beta) = 0$$

This would correspond to:

Dose	100 mg	200 mg	400 mg	600 mg	800 mg	900 mg
Prior mean DLT rate	9%	12%	17%	22%	29%	36%
Prior median DLT rate	1%	3%	7%	13%	22%	30%

DLT = Dose-limiting toxicity.

For more information on operating characteristics of the prior, see [Appendix V](#).

Posterior distribution and the recommended next dose level will be calculated using R version 3.1.2 or higher with library package bcrm [\(38\)](#) or package CRMPack or EAST version 6.4 or higher.

At interim analysis, after end of dose escalation, and main analysis, the number and proportion of subjects experiencing DLTs will be reported by dose level, based on observations during the first treatment cycle. Posterior probabilities (2.5%, 25%, 50%, 75%, and 97.5% quantiles) will be estimated.

The Dose Escalation Analysis Set will be used for this analysis.

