## 8.2 Definition of Analysis Sets and Subgroups

The analysis sets of subjects whose data will be included in the analyses described in this IAP are defined in [Table 1](#).

**Table 1** Analysis Sets

Population	Description
Screening (SCR)	All subjects who sign informed consent.
DLT	All subjects who received at least one dose of study intervention and meet at least one of the following criteria: 

- Received at least 5 planned cumulative total daily doses of M4112 in the first cycle (first 28 days) or

- Experienced at least one DLT during the DLT period, regardless of the administered number of doses of study intervention/completion of the DLT period

Safety	The Safety Analysis Set will include all subjects who receive at least 1 dose of study treatment.
Concentration-QTc Analysis Set	The cQTc Analysis Set will include all subjects with at least baseline and one on treatment measurement of time-matched ECG and M4112 plasma concentration collected during the dose-escalation phase.
M4112 Pharmacokinetic	All subjects from the Safety Analysis Set without clinically important protocol deviations/violations or events that would affect PK (see Section 8.1 ). Subjects in the PK Analysis Set must have received at least 1 dose of M4112 and must have sufficient M4112 plasma concentration data to enable the calculation of at least 1 PK parameter. Sufficient concentration data is defined as at least 3 valid, postdose concentration points in the PK profile to obtain any PK parameter.
Pharmacodynamics	All subjects who received at least 1 dose of M4112 and provide the predose and at least 1 postdose sample for Pd assessment.

cQTc = concentration-QTc response; DLT = dose-limiting toxicities; ECG = electrocardiogram;

Pd = pharmacodynamics; PK = pharmacokinetic; QTc = corrected QT interval.

There are no subgroup analyses planned for this study.

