#### Bayesian two-parameter logistic model

Upon completion of the DLT observation period of each cohort, summary statistics of the posterior probability distribution of the true DLT rate (2.5%, 25%, 50%, 75%, and 97.5% quantiles) for each predefined dose level will be updated and estimated according to the logistic model. Using data from all subjects completing the DLT period or experiencing a DLT during this period at the completion of a new cohort (and data from all previous cohorts: DE analysis set), the Bayesian logistic model provides a recommended dose level for the next cohort.

Recommendation is based on a loss function (probabilities of being in 1 of the 4 intervals will be multiplied with a loss term as follows:

$0 * P(\text{target dosing (estimated DLT rate in (0.17-0.35])}) + 1 * P(\text{for over dosing (estimated DLT rate in (0.35-0.67]) or under dosing (estimated DLT rate in [0-0.17])}) + 2 * P(\text{excessive dosing (estimated DLT rate in (0.67-1])})$ .

In addition, only doses with estimated probability of  $\leq 25\%$  that the true DLT rate is more than 35% (overdose control) will be recommended by the model. The recommended dose level resulting from the model for the next cohort is the dose with the lowest loss function from all doses fulfilling the overdose control rule. This Bayesian escalation approach will be used to assist the SMC to select the next dose from a predicted set of acceptable doses, i.e., 100 mg, 200 mg, 400 mg, 600 mg, 800 mg and 900 mg BID. It is possible to choose a dose(s) not within the pre-specified dose-escalation plan. Using a Bayesian model-based design aids the SMC in dosing decisions by providing more information compared to a 3+3 design (e.g., an estimated dose-toxicity curve with confidence information utilizing data on all subjects in DE analysis set at time of analysis).

The model will continue to be updated at each SMC until the SMC has decided to stop dose escalation.

Prior distribution and likelihood are used to calculate the posterior probabilities based on Bayes theorem.

The likelihood is defined based on a binomial distribution, modelling the rate of subjects with at least 1 DLT.

The prior distribution is set-up as follows:

The relationship between dose and toxicity rate is defined by

$$P(DLT|d_j, \alpha, \beta) = \frac{\exp\left(\alpha + \exp(\beta) * \log\left(\frac{d_j}{d_{ref}}\right)\right)}{1 + \exp\left(\alpha + \exp(\beta) * \log\left(\frac{d_j}{d_{ref}}\right)\right)}$$

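### DLT evaluability is defined in three conflicting ways, so a subject who stops in Cycle 1 for a non-DLT toxicity is in or out of the primary analysis depending on the section

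*Protocol*

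**What the plan says.** Three rules are in force for the same analysis set.

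- **Rule A, safety reasons.** The DLT Definition text in the protocol Synopsis and Section 5.1, and Sections 6.2.4 and 8.5.2, say that subjects missing more than 5 planned total daily doses in Cycle 1 "for other than safety reasons are not eligible for DLT assessment, will not be considered in the Bayesian model". By implication, a subject who misses them for a safety reason stays in.
- **Rule B, DLT only.** The Dose Escalation row of protocol Table 13 (Section 8.4) makes the exception narrower: "of the dose escalation part for other than DLT". Table 1 in Section 10 of the SMC analysis plan uses the same words. Section 16.1 of that plan is in line with this rule, since it feeds the model "Using data from all subjects completing the DLT period or experiencing a DLT during this period".
- **Rule C, doses received.** Table 1 in Section 8.2 of the final analysis plan includes a subject who meets either of two criteria: "Received at least 5 planned cumulative total daily doses of M4112 in the first cycle", or "Experienced at least one DLT during the DLT period, regardless of the administered number of doses of study intervention/completion of the DLT period".

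Protocol Section 8.5.2 states Rule A and then closes with "The Dose Escalation Analysis Set will be used for this analysis", which is the Rule B set. Section 9 of the SMC plan reports no changes to the planned analyses. Section 7 of the final plan describes its new definition only as a clarification.

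**The concern.** DLT occurrence is a primary endpoint, and this set supplies both its denominator and the data for the dose-escalation model. Cohorts are usually 3 subjects, so one membership decision can move an observed rate from 1/3 to 1/2.

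The disputed subject is realistic under the protocol's own rules. Section 6.2.3 requires treatment interruption for a QTc increase, while the QTc criterion in Section 6.2.4 needs Grade 3 or higher clinical signs and symptoms. The immune-related event tables in Section 6.5.5.3 withhold M4112 for several Grade 2 events, some until a steroid taper of at least 1 month is finished. Such a subject can miss more than 5 daily doses without a DLT. The documents do not say how often this would happen.

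Rule A counts that subject as a tolerated non-event and Rule B removes the subject. The same data can then give a different DLT rate and, in some cases, a different model recommendation.

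**Working it through.** **1. The rules side by side.** Cycle 1 has 28 total daily doses. Missing no more than 5 means receiving at least 28 − 5 = 23, so a subject who misses more than 5 has received 22 or fewer.

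| Subject in Cycle 1 | Rule A | Rule B | Rule C |
|---|---|---|---|
| Stops because of a DLT | in | in | in |
| No DLT, stops for another toxicity, 5–22 daily doses received | in | out | in |
| No DLT, stops for another toxicity, 1–4 daily doses received | in | out | out |
| No DLT, stops for a non-safety reason, 5–22 daily doses received | out | out | in |

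Rule C agrees fully with neither of the others.

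**2. Reproducing the plan's own figures.** Inputs come from protocol Section 8.5.2 and SMC plan Section 16.1.

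- Model: logit P(DLT at dose d) = α + exp(β) × log(d/900)
- Prior: E(α) = log(0.31/0.69) = −0.8001; E(β) = log((log(0.11/0.89) − log(0.31/0.69)) / log(400/900)) = 0.4647; variances 1.5², covariance 0
- Loss: 1, 0, 1, 2 for DLT rates in [0, 0.17], (0.17, 0.35], (0.35, 0.67], (0.67, 1]
- Admissible doses: P(rate > 0.35) below 0.25
- Recommendation: the admissible dose with the lowest loss

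The posterior was computed by two-dimensional grid integration. Prior mean DLT rates come out at 9/12/17/22/30/36% against the stated 9/12/17/22/29/36%. All 18 recommended doses in Appendix V reproduce, and the interval probabilities agree to about 0.01. For scenario 4b the result is 0.42/0.36/0.20/0.02 against the printed 0.42/0.36/0.21/0.02.

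**3. Keep or remove one non-DLT subject.** Each scenario was rerun with one non-DLT subject removed from one cohort at a time (Rule B) and compared with keeping that subject (Rule A). The number of comparisons is 3 × (1+2+3+4+5+6) = 63. Four change the recommendation, all with the removal in the current cohort and at least one DLT there:

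| Scenario | Kept | Removed | P(rate > 0.35), kept vs removed |
|---|---|---|---|
| 1a, 100 mg | 1/3 → 100 mg | 1/2 → no admissible dose | 0.244 vs 0.367 at 100 mg |
| 4b, 600 mg | 1/6 → 800 mg | 1/5 → 600 mg | 0.225 vs 0.256 at 800 mg |
| 5b, 800 mg | 1/6 → 900 mg | 1/5 → 800 mg | 0.235 vs 0.272 at 900 mg |
| 6a, 900 mg | 1/3 → 900 mg | 1/2 → 800 mg | 0.199 vs 0.293 at 900 mg |

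None of the six zero-DLT scenarios changes, and no removal from an earlier cohort changes anything. At 600 mg and 800 mg, 1/3 and 1/2 give the same recommendation. Outside Appendix V, 2/6 vs 2/5 at 800 mg (lower levels 0/3) also flips, from 800 to 600 mg, with 0.187 vs 0.253 at 800 mg.

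**4. Stability.** Coarser and finer grids move these probabilities by about 0.002 at most, and no recommendation changes.

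**The case against.** The best case against making much of this has five parts.

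- **The output is advisory.** The SMC may choose another dose and defines the MTD, and the Sponsor decides. The SMC also receives patient profiles with all adverse events, dosing and withdrawal reasons, so a toxicity dropout is visible whether or not the model counts it. This stands and limits the consequence.
- **The effect is uncommon.** Protocol Section 8.1 does not expect frequent DLTs, and with none in the current cohort no scenario changes. Scenario 4b (0.256) and the 2/5 case (0.253) sit close to the 0.25 limit. This also stands.
- **The SMC plan is internally consistent.** Its Table 1 and Section 16.1 both follow Rule B. But it derives from a protocol that states Rule A four times, and it declares no change. Its own DLT-definition section is partly blacked out and may address the point. The conflict described here rests only on visible text.
- **Safety reasons may be loose wording for a DLT.** That is possible, but nothing says so, and the protocol distinguishes the two elsewhere.
- **The final plan replaces the set.** It does settle which toxicity exception applies at the final analysis. It also switches from doses missed to doses received, which admits subjects whom both other rules exclude.

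**Conclusion.** The conflict is real and should be fixed. For a subject who misses more than 5 daily doses because of a non-DLT toxicity, the plan does not determine membership of the primary-endpoint set. The threshold in the final analysis plan adds a second inconsistency, for subjects who received 5 to 22 daily doses.

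The size is modest. One such subject changes the model recommendation in 4 of 18 Appendix V scenarios, or 4 of 63 single removals. It happens only with a DLT in the current cohort, and Rule A gives the higher dose each time. This assumes the stated prior, loss and overdose rule, 0/3 at all lower levels, and a single disputed subject.

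A reader might infer that a non-DLT dropout routinely alters the escalation, or that doses in this trial were recommended wrongly. The documents support neither. Most removals change nothing, the frequency of such dropouts is not given, and the plans contain no trial data. The final plan is dated after the decision to terminate and after Part IA was completed, so its wording cannot affect earlier SMC advice. What it still governs is the final DLT table and the posterior quantiles.

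**What to change.** - Reconcile the protocol Synopsis, Sections 5.1, 6.2.4 and 8.5.2, Table 13, SMC plan Table 1 and final plan Table 1 to one definition in identical words. Bring the data description in SMC plan Section 16.1 into line with it.
- Say whether the threshold counts total daily doses missed or received.
- State explicitly whether a subject who misses more than 5 daily doses for a non-DLT toxicity is in the set and, if so, that the subject counts as a non-event.
- In the final analysis, report DLT counts and posterior quantiles by dose level under the alternative reading as a sensitivity line.

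The cost is wording in the protocol and both analysis plans. If the protocol is not amended, an entry in Section 7 of the final plan should set out the change and its reason. The sensitivity line needs one rerun of the existing model code and one extra table line. Both can be done before database lock.

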## 8.5 Description of Statistical Analysis

### 8.5.1 General Considerations

All analyses will be prepared by study part (eg, monotherapy escalation, CCI and dose level and will be described in detail in the iAP).

There is no formal significance level for this study and all analyses are considered descriptive.

In general, continuous variables will be summarized using number of subjects (n); mean, standard deviation; median, 25th Percentile to 75th Percentile (Q1-Q3), minimum, and maximum. Categorical variables will be summarized using frequency counts and percentages.

The calculation of proportions will be based on the number of subjects in the analysis set of interest, unless otherwise specified in the study iAP.

## Baseline

In general, the last nonmissing measurement prior to the first study treatment will serve as the baseline measurement.

